## 5. STUDY POPULATION

### 5.1. Subject Disposition

Subject disposition will be tabulated by treatment group and overall and will include the number randomized, the number randomized but not treated, the number treated in total, the number of subjects in the specified analysis population, the number of subjects who completed Month 18 Visit, the number of subjects who completed Month 18 Visit with a biopsy, the number of subjects who withdrew from investigational product but remained in the study, the number of subjects who withdrew from study prior to completing the study and reason(s) for withdrawal, and the number of subjects who were contacted for follow-up.

Disposition summaries will be presented for each analysis population and will be tabulated by treatment group and overall.

Subject enrollment by study site will be tabulated by treatment group and overall.

A by-subject data listing of study completion information including the reason for premature study withdrawal, if applicable, will be presented.

### 5.2. Demographics and Baseline Characteristics

Demographic variables will include the following:

- Age and groups (<65 years, ≥65 years, ≥75 years) at the time of informed consent
- Gender
- Race
- Ethnicity
- Geographic Region: North America, Europe, and ROW (including Asia as a subgroup)

Other baseline characteristics will include the following:

- Liver fibrosis stage (NASH CRN scoring criteria) by central read and consensus read as available.
- Liver fibrosis stage (Modified Ishak scoring criteria)
- Hepatocellular Ballooning by central read and consensus read as available.
- Lobular Inflammation by central read and consensus read as available.
- Steatosis by central read and consensus as available
- Nonalcoholic fatty liver disease activity score (NAS: <6, ≥6)
- Weight (kg)
- Height (cm)
- BMI (kg/m^2): Continuous and Categorical: ( <30 kg/m^2, ≥30 kg/m^2, <35 kg/m^2, ≥35 kg/m^2 Diabetes Status (Yes/No)

- Diabetes Status (Yes/No)
- Hemoglobin A1c (HbA1c;  $\leq 5.6\%$ , 5.7-6.4%,  $\geq 6.5\%$ )
- Low density lipoprotein (LDL: mg/dL) ( $\geq 100$  mg/dL,  $\geq 190$  mg/dL)
- Triglycerides (mg/dL) ( $\geq 150$  mg/dL)
- High density lipoprotein (HDL; mg/dL) ( $< 40$  mg/dL [men] or  $< 50$  mg/dL [women])
- Baseline Concomitant Medication Use
  - Lipid-lowering medications, including Statins
  - Statins only
  - Antihypertensive medications
  - Antidiabetic medications
  - Thiazolidinedione (TZD) only
  - Vitamin E
  - Anticoagulants/antiplatelets
  - Bile acid sequestrants
- Baseline Caffeine Intake
- Baseline Alcohol Consumption as assessed by AUDIT Questionnaire (AUDIT Score  $\leq 7$ ,  $> 7$ )
- Baseline Smoking Habits and Status
- [REDACTED]

Liver biochemistry, liver function and estimated glomerular filtration rate (eGFR) results at baseline will be summarized as continuous variables and as frequencies for categorizations. The upper limit of normal (ULN) for liver functions suggested by FDA will be used: ALT – 30 U/L, AST – 35 U/L, Total Bilirubin – 1.25 mg/dL, Conjugated (Direct) Bilirubin – 0.3 mg/dL, ALP – 120 IU/L.

- eGFR (chronic kidney disease epidemiology collaboration [CKD-EPI] calculation) and groups (G1/Normal, G2, G3)
- ALT and AST:  $\leq$  upper limit of normal (ULN),  $>ULN$  to  $\leq 3x$  ULN,  $>3x$  ULN
- Total Bilirubin and Conjugated (Direct) Bilirubin:  $\leq ULN$ ,  $>ULN$
- ALP and GGT:  $\leq ULN$ ,  $>ULN$
- Model for end stage liver disease (MELD) Score

Demographics and Baseline characteristics will be summarized and presented by treatment group and overall for the, ITT, mITT, Full Efficacy Analysis, PP, Safety, and PK Populations.

For continuous measures, number of subjects, mean, SD, median, Q1, Q3, minimum, and maximum will be presented. For categorical measures, number and percentage of subjects will be presented. No inferential statistical comparisons will be performed.

All demographic and Baseline characteristic data will be presented in by-subject data listings.

### **5.3. Baseline NASH Disease Characteristics**

Baseline NASH disease characteristics will be summarized using data collected from the NASH Disease History eCRF. Variables from the NASH Disease History eCRF include the following:

- Age at NASH diagnosis
- Duration of NASH in years at time of informed consent

Baseline NASH disease characteristics will be summarized and presented by treatment group and overall for the ITT, mITT, Full Efficacy Analysis, PP, Safety, and PK Populations. For these continuous measures, the number of subjects, mean, SD, median, Q1, Q3, minimum, and maximum will be presented. No inferential statistical comparisons will be performed.

Baseline NASH disease characteristics will be presented in by-subject data listings.

### **5.4. Medical and Cardiovascular Medical History**

Verbatim terms on electronic case report forms (eCRFs) will be mapped to preferred terms (PT) and system organ classes using Medical Dictionary for Regulatory activities (MedDRA).

Medical history will be summarized by SOC, PT, and treatment group using the Safety Population. Summaries will be ordered by descending order of incidence of SOC and PT within each SOC.

The following cardiovascular (CV) variables from the CV Medical History eCRF will be summarized by preferred term:

- Types and number of CV conditions/events
- Types and number of CV treatment procedures received

Lastly, separate summaries will be provided by SOC and PT for the number and percentage of subjects with medical history in the following categories:

- Pruritus
- Hepatic Disorders
- Gallbladder disease and Related Complications
- Pancreatitis
- Glycemic control
- Dyslipidemia
- Renal Disorders
- Urolithiasis

Medical and CV medical history will be presented in a by-subject data listing.

## **5.5. Protocol Deviations**

The Investigator is not permitted to deviate from the protocol in any significant way without notification to the Sponsor (or designee) as described in the protocol.

All eligibility deviations specified in the protocol will be considered major deviations and subjects meeting any of these deviations will not be included in the PP Population. Major on-study protocol deviations that could potentially affect the efficacy or safety conclusions of the study will be identified through programming and identifying selected categories from the list of protocol deviations collected during the study:

- Investigational product dosing, including subjects who receive treatment different from what they were randomized to.
- Taking investigational product after bariatric surgery (gastric bypass)

All major protocol deviations will be summarized and listed by treatment group.

## **5.6. Impact of COVID-19 Pandemic**

The percentage and number of subjects with protocol deviations related COVID-19 will be summarized by randomized treatment and by deviation type in Full Efficacy Analysis Population and Safety Population.

The incidence of COVID-19 related TEAEs, serious TEAEs, severe TEAEs, relationship to OCA and fatal TEAE will be summarized by treatment group, by SOC and PT in Safety Population. A listing of subjects with the COVID-19 related TEAEs will be generated.

## **6. EFFICACY ANALYSES**

Primary efficacy will be based on the ITT Population. The sections below provide further details on the methods and populations to be used in analyzing each of the efficacy endpoints. All efficacy endpoints will be presented in by-subject data listings.

### **6.1. Adjustments for Covariates**

For histological endpoints; primary, secondary, and exploratory endpoints; the comparison between treatment groups will be performed using CMH test stratified by the randomization strata (type 2 diabetes at enrollment [yes/no] and use of TZDs/glitazones or vitamin E at baseline [yes/no]).

For continuous secondary and exploratory endpoints, change from baseline and percentage change from baseline over time will be analyzed using the MMRM model with treatment, baseline, visit, visit by treatment interaction, and stratification factors to be included in the model.

## **6.2. Handling of Subject Discontinuations and Missing Data**

Subjects who discontinue investigational product for any reason other than withdrawal of consent are expected to continue in the study until study termination.

In order to determine the effect of missing data on the analysis, efficacy endpoints will be analyzed using different methods of imputation as described below.

### **6.2.1. Quantitative Endpoints**

For exploratory efficacy endpoints utilizing an analysis of covariance (ANCOVA), MMRM model, observed cases will serve as the primary analysis.

### **6.2.2. Responder Endpoints**

For the primary endpoint analysis, the centrally read screening biopsy will be used as baseline histology data. The Month 18 or post-baseline biopsy that is centrally read as part of the paired read (ie, paired with a new slide from the screening/baseline biopsy tissue to minimize temporal bias) will be compared with the baseline biopsy (screening) to determine efficacy, ie, responder status for primary endpoints as well as other histology efficacy endpoints. Additional analyses may be conducted using the baseline biopsy slide that was used as part of the paired reading for primary endpoints as well as other histology efficacy endpoints.

The protocol requires a Month 18 biopsy even for subjects who discontinued treatment but are on-study (in addition to the end of treatment biopsy, if applicable, by the protocol). For each post-baseline biopsy, a paired reading will be performed. If a subject has more than one paired reading by the Month 18 Visit, only one paired reading will be reported in Electronic Data Capture (EDC) based on the biopsy preceded by the longest (and least interrupted) investigational product exposure.

[figure not shown]
The biopsy consensus based read methodology by a three pathologists panel will be implemented for all baseline and all subsequent histology data using whole slide image (WSI) technology. The stained slides were digitized (scanned by ICON and other vendor) and the WSI were sent to PathAI (vender) to be read by pathologists using the consensus method using their research platform. In cases where a previously stained slide was either missing OR could not be read by the Consensus panel, a new slide was requested to be stained, scanned and read. A two-stage approach will be utilized to reach a consensus. At stage one, all three pathologists at each panel will independently read each subject's slide image and enter the results in the database. If the two pathologists matched the score for a specific component, it is chosen as the consensus score for the component. If the scores from all 3 pathologists for a specific parameter are discordant, a single consensus score will be provided by a joint panel read at stage two and flagged as Joint panel decision (refer to histology manual).

Panel A of 3 pathologists will read images of slides stained with H&E to characterize NAS (ballooning, inflammation, steatosis) score and Panel B pathologists will read images of slides stained with Trichrome to characterize NAS CRN fibrosis score. The endpoint regarding the improvement or worsening of fibrosis stage and NASH will be derived based on the results from the consensus values at baseline and any post-baseline liver biopsy collection.

For the analyses of histological efficacy endpoints, in which subjects are classified as either responders or non-responders (binary outcome), any subject who discontinues from the study prior to the Month 18 biopsy Visit and does not have a post-baseline biopsy assessment will be considered a non-responder. Biopsies collected for subjects who discontinued treatment before the Month 18 visit will be included in the Month 18 Interim Analysis of histological endpoints regardless of the timing of the biopsy.

Similar conventions and statistical methodologies will be used for analyses of other exploratory histological-based responder analyses. Responder endpoint analyses will be carried out for the primary and secondary endpoints using the ITT, mITT, Full Efficacy Analysis Population and PP Populations.

A complete summary and description of the analysis plan and populations for histological data based on the consensus method can be found in SAP Addendum V2 (dated 25 Apr 2022).

[figure not shown]

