
Additional information regarding the data cutoff date for the Month 18 Interim Analysis population will be defined in the SAP.

Analyses**Efficacy Analyses:**

All efficacy hypothesis testing will be based on the ITT population including only fibrosis stage 2 and stage 3 subjects. Supportive analyses will be conducted using PP population and all fibrosis stages (Full Analysis Population).

The 2-sided alpha allocated to all testing in this single study will be 0.05. The histological endpoints will be tested at the Month 18 Interim Analysis with alpha level of 0.02. The primary clinical outcomes endpoint will be tested with a minimum alpha level of 0.03 and this may be augmented by recycled alpha from the Month 18 interim analysis.

For the Month 18 Interim Analysis, multiplicity adjustment will be implemented to control the type 1 error. Details will be provided in the SAP.

Primary Efficacy Analysis at the Month 18 Interim Analysis:

The primary efficacy analysis for fibrosis improvement at Month 18 will test the following hypotheses using the ITT population (the ITT population for the Month 18 Interim Analysis is not the same as that for the overall study and is defined in the SAP):

- H_{01} : The percentage of subjects with fibrosis improvement by at least 1 stage with no worsening of NASH is equal between placebo and OCA 25 mg.
- H_{11} : The percentage of subjects with fibrosis improvement by at least 1 stage with no worsening of NASH is different between placebo and OCA 25 mg.

The primary efficacy analysis for the resolution of NASH will test the following hypotheses:

- H_{02} : The percentage of subjects with resolution of NASH and no worsening of fibrosis is equal between placebo and OCA 10 mg.
- H_{12} : The percentage of subjects with resolution of NASH and no worsening of fibrosis is different between placebo and OCA 10 mg.

The primary efficacy analyses at the Month 18 Interim Analysis will compare placebo and OCA using a Cochran–Mantel–Haenszel test stratified by the randomization strata (presence of type 2 diabetes at enrollment [yes/no] and use of TZDs/glitazones or vitamin E at baseline [yes/no]). Subjects with missing histology results at Month 18, will be considered non-responders. Post-baseline biopsies at early termination visit (prior to Month 18) will be included in the analysis regardless of the timing of the biopsy.

Secondary Efficacy Analyses at the Month 18 Interim Analysis:**Histology Analysis**

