16.6.3. Responder Endpoints

For the analyses of the primary and key secondary histological efficacy endpoints, in which subjects are classified as either a responder or a non-responder (binary outcome), any subject who does not provide any assessment at the specified timepoint and after baseline for the defining of response will be considered to be a non-responder. That is, for the percentage of responders, the subject will be included in the denominator and will not contribute to the numerator. Subjects who early terminate before Month 18, biopsy results at the time of early termination, if available, will be included in Month 18 histological endpoints analyses.

A completer analysis will also be conducted, excluding those subjects who do not provide an assessment at the specified timepoint for the defining of response. That is, for the percentage of responders, the subject will not be included in the numerator or the denominator.

Additional sensitivity analysis will be described in the SAP.

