#### 4. GENERAL STATISTICAL METHODS

Individual subject data obtained from electronic case report forms (eCRFs), local laboratories, central laboratories, external sources, and any derived data will be presented in data listings by subject. All data listings that contain an evaluation date will contain a relative study day. Pre-treatment and on-treatment study days are numbered relative to the day of the first dose of investigational product which is designated as Day 1. The preceding day is Day -1, the day before that is Day -2, etc.

For categorical variables, summary tabulations of the number and percentage of subjects within each category (with a category for missing data) of the parameter will be presented. Percentage calculations will be based on non-missing data unless otherwise specified.

In response analysis [yes/no] of histological endpoints, the comparison between treatment groups will be performed using CMH test stratified by the randomization strata (type 2 diabetes at enrollment [yes/no] and use of TZDs/glitazones or vitamin E at baseline [yes/no]).

For continuous variables, the number of subjects, mean, standard deviation (SD), standard error of the mean (SEM), median, 25th and 75th quartiles, minimum, and maximum values will be presented.

Longitudinal summaries of continuous variables will present absolute values, change, and percentage change from baseline at each post-baseline visit.

For continuous endpoints satisfying normality assumptions, change from baseline and percentage change from baseline over time will be analyzed using mixed-effect repeated measures (MMRM) model with treatment, baseline, visit, visit by treatment interaction and stratification factors to be included in the model. An unstructured covariance model will be used. If the computational algorithm fails to converge, an appropriate covariance structure will be selected. Estimates of least-square (LS) means, standard errors will be presented by treatment group. Unless indicated otherwise 95% CIs will be provided for efficacy endpoints by treatment group.

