## **APPENDIX A. DATA CONVENTIONS AND STANDARD PROGRAMMING**

### **DATA PRESENTATION CONVENTIONS:**

The precision of original measurements will be maintained in summaries, when possible. Minimum and Maximum will be presented with the same decimal places as the raw data. Means, medians, SEMs, and SDs will be presented with an increased level of precision, where means, medians, and percentiles will be presented to one more decimal place than the raw data, and the SEMs and SDs will be presented to two more decimal places than the raw data. In general, the decimal places should not exceed 3 decimal places, unless appropriate.

For tables where rounding is required, rounding will be done to the nearest round-off unit. For example, when rounding to the nearest integer, values  $\geq XX.5$  will be rounded up to  $XX + 1$  (eg, 97.5 will round up to 98), while values  $< XX.5$  will be rounded down to  $XX$  (eg, 97.4 will round down to 97).

Percentages based on frequency counts will be based on available data, and denominators will generally exclude missing values. Percentages based on frequency counts will be presented as whole numbers (no decimal places), and values less than 1% will be presented as “<1%.” Values less than 100% but that round up from 99.5% to 100% will be presented as “>99%.”

Quantitative laboratory tests containing less than (<) and greater than (>) symbols are test results that are below and above quantifiable limits, respectively. In order to retain these values for analysis purpose, the following imputations will be done within the analysis datasets:

For laboratory test results that are below the quantifiable limit:

Imputed laboratory results = (numeric portion of the result) x 0.9.

For laboratory test results that are above the quantifiable limit:

Imputed laboratory results = (numeric portion of the result) x 1.1.

Date variables will be formatted as DDMMMYYYY for presentation. Time will be formatted in military time as HH:MM for presentation.

All output will be incorporated into Microsoft Word rich text format (.rtf) files, sorted, and labeled according to the ICH recommendations, and formatted to the appropriate page size(s).

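### SAP 6.2.2 scores only subjects who left the study as non-responders, so on-study subjects without a biopsy fall outside the rule the protocol applies to them

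*SAP*

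**What the plan says.** The protocol states its rule twice, and neither statement depends on whether the subject is still on study. In the Synopsis: "Subjects with missing histology results at Month 18, will be considered non-responders". In Section 16.6.3, for the primary and key secondary histological endpoints, a non-responder is "any subject who does not provide any assessment at the specified timepoint and after baseline for the defining of response", and for the percentage of responders "the subject will be included in the denominator and will not contribute to the numerator". Both places allow a biopsy taken at early termination to count. Leaving subjects out is a second analysis: "A completer analysis will also be conducted, excluding those subjects who do not provide an assessment at the specified timepoint".

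SAP 6.2.2 words the rule differently. The non-responder is "any subject who discontinues from the study prior to the Month 18 biopsy Visit and does not have a post-baseline biopsy assessment". The next sentence brings in biopsies from subjects who stopped treatment before Month 18, whatever their timing.

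Two general SAP conventions bear on subjects whom no specific rule covers. Section 4: "Percentage calculations will be based on non-missing data unless otherwise specified". Appendix A, on data presentation: "denominators will generally exclude missing values".

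**The concern.** The SAP joins two conditions: the subject has left the study before the Month 18 biopsy visit, and has no post-baseline biopsy. A subject who remains on study and is never biopsied meets the second condition but not the first, so the stated rule does not reach that subject.

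The SAP foresees this group. Section 6.2.2 notes that subjects off treatment but on study still owe a Month 18 biopsy. Section 5.1 counts Month 18 completers with a biopsy separately from all Month 18 completers. Protocol 7.7 and 7.9 expect subjects who stop product to stay in the study.

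At stake is what the ITT responder rate means. If these subjects are left out, each arm's rate is taken over biopsied subjects plus early leavers, and the comparison is no longer the one the protocol made primary. Differential loss is conceivable: Protocol Table 4 requires stopping product for severe pruritus while visits continue, and Protocol 5.3 reports pruritus in 23% against 6% in the earlier Phase 2 study. The documents give no rate of missing biopsies by arm.

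**Working it through.** No figure in the plan depends on this wording, so there is none to reproduce. The check sets the rules side by side and then illustrates the size.

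**Step 1: classify the subject types.**

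| Subject, no evaluable post-baseline biopsy | Protocol Synopsis / 16.6.3 | SAP 6.2.2 |
|---|---|---|
| Left the study before Month 18 | Non-responder, in denominator | Non-responder |
| Still on study, on or off drug | Non-responder, in denominator | Not covered by the rule |

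The two documents agree only if the second row is empty.

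**Step 2: where the second row goes.** SAP 6.2.2 does not say. If the conventions in SAP Section 4 and Appendix A are applied, the subject leaves both numerator and denominator.

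**Step 3: size.** Let r be the response rate among biopsied subjects and m the share of the arm on study without a biopsy, taking every other subject as biopsied. Excluding those without a biopsy gives a rate of r. Scoring them as non-responders gives r(1 − m). The treatment difference under exclusion exceeds that under the protocol rule by r_OCA × m_OCA − r_placebo × m_placebo.

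All rates here are assumptions: r = 25% on OCA and 13% on placebo, so exclusion always gives 25 − 13 = 12.0 points.

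| Missing, OCA / placebo | OCA, protocol rule | Placebo, protocol rule | Difference | Excess under exclusion |
|---|---|---|---|---|
| 8% / 8% | 25 × 0.92 = 23.0% | 13 × 0.92 = 11.96% | 11.0 points | 1.0 |
| 10% / 5% | 25 × 0.90 = 22.5% | 13 × 0.95 = 12.35% | 10.2 points | 1.9 |
| 15% / 8% | 25 × 0.85 = 21.25% | 13 × 0.92 = 11.96% | 9.3 points | 2.7 |

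(Before rounding, the middle row is 10.15 and 1.85.)

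The excess is not bound to favour OCA. With these response rates it changes sign once the placebo share missing is more than 25/13 = 1.92 times the OCA share.

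**Step 4: a second illustration, on power.** Assume response among biopsied subjects of 20% on OCA and 10% on placebo, 250 per arm (the minimum of 750 divided by three) and two-sided alpha 0.01 (the critical value for the smaller P-value in SAP 6.3.1). With 5% missing in both arms, power is 68.5% under exclusion and 68.0% under the protocol rule. With 10% missing on OCA and 5% on placebo it is 67% and 57%. The choice of rule matters little when missingness is equal and more when it is not.

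**The case against.** The strongest reply is that exclusion is inferred and not written. The Section 4 sentence sits in a paragraph on summary tables, with responder analyses described separately, and the Appendix A sentence is a presentation convention qualified as general. SAP 6.2.2 itself treats response as binary, with no third, excluded class. The Month 18 ITT definition in SAP 3.4.1 requires no biopsy, the Per Protocol set adds one as a condition, and the mITT set removes certain discontinuers without a biopsy, which presupposes that ITT holds them. This stands as evidence that the authors may have meant to keep these subjects. It does not supply the missing rule.

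Second, the text of SAP 6.2.3 (Sensitivity Analyses) cannot be seen, nor can SAP Addendum V2.0, to which 6.2.2 refers for the consensus-read histology. Either may deal with these subjects. This stands and limits the conclusion.

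Third, the group may be small. Protocol 7.7 and 9.9.9 call for a biopsy at end of treatment, the SAP accepts it whatever its timing, and 6.2.2 arranges a new slide where one was missing or unreadable by the consensus panel. Among those off drug, mainly subjects with neither an end-of-treatment nor a Month 18 biopsy remain. This stands too.

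Fourth, SAP Section 1 says the Month 18 analyses were done for the original submission. However, SAP 6.4.5 has all Month 18 histological endpoints analysed at End of Study, so the wording is still in use.

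**Conclusion.** The mismatch is real and rests on the wording alone: the protocol rule covers all missing Month 18 histology, and the SAP rule covers only subjects who also left the study. The supplied text does not declare this as a departure. The key-changes table in SAP Section 11 does not mention it, although that table compares with SAP V1.0 and so does not show when the wording entered.

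A reader might go further and infer that the SAP orders these subjects out of the ITT percentages, or that the Month 18 results already reported are inflated in favour of OCA. The documents support neither. Exclusion follows only if the general defaults are applied to a case on which 6.2.2 is silent, and no document says how many such subjects there were or in which arm.

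The size is therefore unknown. Under the assumed response rates of 25% and 13%, the treatment difference would be larger by 1.0 to 2.7 points under exclusion for the three missingness patterns shown. The point deserves correction because it touches the primary histological endpoints and is cheap to close.

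**What to change.** Reword the non-responder sentence in SAP 6.2.2. For Month 18 histological endpoints, any subject in the Month 18 ITT cohort (at least one dose, stage 2 or 3, randomized by 15 July 2017) without an evaluable Month 18 biopsy, or an early-termination or end-of-treatment biopsy that the protocol allows, is a non-responder and stays in the denominator, whether or not still on study. Keep the completer analysis as supportive.

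The cohort limit is essential and should be repeated in SAP 6.4.5 for the End of Study analysis. The End of Study ITT set in SAP 3.4.2 has no randomization cut-off. Protocol 9.9.7 releases subjects randomized on or after 16 July 2017 who had no Month 18 biopsy from having one, unless progression to cirrhosis is suspected. Without the limit, those subjects would be scored as failures for a biopsy that was not required.

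If SAP 6.2.3 or Addendum V2.0 already contains this rule, a cross-reference in 6.2.2 is enough. The cost is a sentence in 6.2.2, the matching limit in 6.4.5 and slightly lower reported response rates.
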